8.6.3.7 Time to improvement based on EXACT-PRO total score

All EXACT-PRO rolling average results available at Day 3, 5, 7, 10, 14 and 29 will be summarised at each visit by treatment regimen using descriptive statistics. The improvements (changes) in EXACT-PRO rolling average from baseline (Day 1 pre-dose) will also be summarised at Day 3, 5, 7, 10, 14 and 29 by treatment regimen.

MMRM analysis using an unstructured covariance matrix and the Kenward-Roger adjustment for the denominator degrees of freedom will be performed for statistical comparison of treatment regimens with improvement in EXACT-PRO rolling average as an outcome. Model will consider treatment, severity of airflow limitation at baseline, blood eosinophils (%) value at baseline, time from start of current COPD exacerbation to first IMP dosing, presence of cardiovascular comorbidities at screening and COPD exacerbation treatment at screening as fixed effects and baseline EXACT-PRO Rolling Average score as covariate. In addition the baseline score-by-visit and the treatment-by-visit interactions will be included in the model.

LSMEAN and standard error (SE) of each treatment regimen, difference of LSMEANS between treatment regimens and their associated two-sided 95% CIs and corresponding two-sided P-values for Day 3, Day 5, Day 7, Day 10, Day 14 and Day 29 will be estimated by the model. P-values of the effects will also be presented.

The unstructured covariance matrix (which does not presume a particular correlation structure for repeated measurements within patients over time) will be used to adjust for the within-patient error variance covariance. In case model fails to converge, other covariance matrix structures will be considered in the sequence of Ante-dependence, Toeplitz, Heterogeneous AR(1), Heterogeneous Compound Symmetry, and Compound Symmetry.

Similar descriptive analysis and MMRM analysis as above will be performed for each of the 3 EXACT-PRO subscores.

The following figure will be produced for the EXACT-PRO total score and each of the 3 EXACT-PRO subscores:

- Mean EXACT-PRO Rolling Average over time for Day 1 to Day 29 by treatment regimen

Improvement based on EXACT-PRO total score is defined as a decrease in the Rolling Average EXACT score ≥ 9 points from the previous day's Maximum Observed Value during an event.

Time to EXACT-PRO improvement will be analysed using the Kaplan-Meier method. Patients without any EXACT-PRO improvement from baseline over the observed period (Day 1 to Day 29) or who are discontinued before reaching it will be considered as “censored” patients.

For the following study periods: Day 1, Days 2-3, Days 4-5, Days 6-7, Days 8-10, Days 11-14 and Days 15-29, the number of patients without an improvement of EXACT-PRO total score from baseline at the beginning of the period, the cumulative number of patients with an EXACT-PRO improvement at the end of the period and the probability of improvement at the end of the period with the associate two-sided 95% CIs will be presented by treatment regimen. The point estimates and the relative two-sided 95% CIs will be presented by treatment regimen for the 75th, 50th and 25th percentiles. A Kaplan-Meier plot will also be presented. Comparisons between treatment regimens will be performed by means of the log-rank test. The p-values of the pairwise log-rank test comparisons will be displayed on the figure.

8.6.3.8 Time to recovery based on EXACT-PRO total score

Recovery based on EXACT-PRO total score is defined as the first day in which a patient experiences a persistent, sustained improvement in their condition over the observed period (Day 1 to Day 29). Improvement (as defined above) must be present for 7 consecutive days. The first day of the 7-day period is designated as the first day of Recovery.

Time to EXACT-PRO recovery will be analysed using the Kaplan-Meier method. Patients without any EXACT-PRO recovery from baseline over the observed period (Day 1 to Day 29) or who are discontinued before reaching it will be considered as “censored” patients.

For the following study periods: Day 1, Days 2-3, Days 4-5, Days 6-7, Days 8-10, Days 11-14 and Days 15-29, the number of patients without a recovery of EXACT-PRO total score from baseline at the beginning of the period, the cumulative number of patients with an EXACT-PRO recovery at the end of the period and the probability of recovery at the end of the period with the associate two-sided 95% CIs will be presented by treatment regimen. The point estimates and the relative two-sided 95% CIs will be presented by treatment regimen for the 75th, 50th and 25th percentiles. A Kaplan-Meier plot will also be presented. Comparisons between treatment regimens will be performed by means of the log-rank test. The p-values of the pairwise log-rank test comparisons will be displayed on the figure.

8.6.3.9 Standardised AUC of EXACT-PRO over time

The standardised AUCs of EXACT-PRO (Day 1 to Day 3, Day 1 to Day 5, Day 1 to Day 7, Day 1 to Day 10, Day 1 to Day 14, Day 1 to Day 29) will be derived and summarised with standard descriptive statistics by treatment regimen.

The standardised AUC from Day 1 to Day 14 will be analysed using an ANCOVA model estimating the effect up to Day 14, using OC, including treatment, severity of airflow limitation at baseline, blood eosinophils (%) value at baseline, time from start of current COPD exacerbation to

first IMP dosing, presence of cardiovascular comorbidities at screening and COPD exacerbation treatment at screening as fixed effects and baseline EXACT-PRO Rolling Average score as a covariate.

The ANCOVA model results will be presented with LSMEAN and standard error (SE) of each treatment regimen as well as the adjusted mean difference between treatment regimens at Day 14 and associated two-sided 95% CIs. Each pairwise treatment regimen comparison will be tested at an alpha level of 5%. P-values of the effects will also be presented.

A similar ANCOVA model will be used to analyse the standardised AUC of EXACT-PRO from Day 1 to Day 7 and from Day 1 to Day 10.

All the analyses above will be repeated for each of the 3 EXACT-PRO subscores AUCs.

8.6.3.10 Change from Baseline at each inter-visit period and over the entire period of the study in the average EXACT-PRO total score and domain scores

All EXACT-PRO rolling average scores available will be summarised at baseline (Day 1 pre-dose) and at specific timepoints during the Acute Exacerbation Phase (Day 3, Day 5, Day 7, Day 10, Day 14) by treatment regimen using descriptive statistics. The improvements (changes) in EXACT-PRO rolling average score from baseline (Day 1 pre-dose) will also be summarised at these timepoints by treatment regimen (See SAP Section 8.6.3.7). Considering Stabilisation Phase, All EXACT-PRO rolling average scores available will be summarised at baseline (Stabilisation Phase), Day 29 (end of Week 4), Day 57 (end of Week 8), Day 85 (end of Week 12), Day 113 (end of Week 16), Day 141 (end of Week 20), Day 169 (end of Week 24) and Week 26 Visit during the Stabilisation Phase by treatment regimen using descriptive statistics. The changes in EXACT-PRO rolling average score from baseline (Stabilisation Phase) will also be summarised at these timepoints by treatment regimen.

The following figures will be produced for the EXACT-PRO rolling average score:

- Mean EXACT-PRO rolling average score over time by treatment regimen (Acute Exacerbation Phase and Stabilisation Phase separately).
- Mean EXACT-PRO rolling average score change from baseline over time by treatment regimen (Acute Exacerbation Phase and Stabilisation Phase separately).

The same analysis as above will be performed for each of the 3 EXACT-PRO subscores.

8.6.3.11 Number of COPD-related exacerbations during the study derived from 'Acute Exacerbation COPD' form of the eCRF

COPD-related exacerbations during the study derived from the 'Acute Exacerbation COPD' form of the eCRF will be considered for this analysis.

Only COPD exacerbations with symptoms start date \geq first study treatment intake on the form will be included in the analysis. The ‘date when symptoms started’ recorded on the form will be defined as the start date of the COPD exacerbation.

The number and the percentage of patients with COPD exacerbations, the number of COPD exacerbations and the total follow-up time in years will be summarised by treatment regimen.

The rate of COPD exacerbations per patient per year will be calculated for each treatment regimen using a weighted approach (which consists of pooling all patients of a treatment regimen and dividing the total number of COPD exacerbations by the total follow-up time).

The number and the percentage of patients with COPD exacerbations, the number of COPD exacerbations and the COPD exacerbation rate per patient per year as above will also be presented by treatment regimen for each of the following types of COPD exacerbation:

- Mild COPD exacerbations (intensity recorded as ‘Mild’ on the form)
- Moderate COPD exacerbations (intensity recorded as ‘Moderate’ on the form)
- Severe COPD exacerbations (intensity recorded as ‘Severe’ on the form)
- Moderate/Severe COPD exacerbations (intensity recorded as ‘Moderate’ or ‘Severe’ on the form)
- COPD exacerbations resulting in death (i.e. COPD-related deaths; serious criteria ‘Results in death’ ticked on the form)
- COPD exacerbations requiring hospitalisation (i.e. serious criteria ‘Requires in-patient hospitalisation or prolongs existing hospitalisation’ ticked on the form).

Additionally (and more generally), the number (%) of patients with COPD exacerbations and the number of COPD exacerbations will be presented by treatment regimen for each of the following category:

- COPD exacerbations treated with systemic corticosteroids only (box ticked on the form)
- COPD exacerbations treated with antibiotics only (box ticked)
- COPD exacerbations treated with systemic corticosteroids and antibiotics (both boxes ticked)
- COPD exacerbations requiring invasive ventilation support (box ticked)
- COPD exacerbations requiring non-invasive ventilation support (box ticked)
- COPD exacerbations requiring Intensive Care Unit (ICU) admission (box ticked)
- COPD exacerbations with each of the following aetiologies: Infection, Environmental pollutants, Extrapulmonary co-morbidities, Concomitant pulmonary co-morbidities, Allergic, Other, Missing (if no aetiology was recorded). A multiple aetiology is possible: in this case the exacerbation will be counted in all the relevant categories.

The proportion of patients with COPD-related exacerbations during the study will be compared between treatment regimens using Pearson’s Chi-square test (or Fisher’s exact test as appropriate)

(two-sided test at 5% alpha level). This comparison will also be made for mild COPD-related exacerbations, for moderate COPD-related exacerbations, for severe COPD-related exacerbations and for moderate/severe COPD-related exacerbations separately.

Finally, the following acute COPD exacerbation characteristics data (from ‘Acute Exacerbation COPD’ form of the eCRF) will be summarised by treatment regimen and overall for ITT and PP populations: duration of acute COPD exacerbation symptoms (days), time until complete recovery from the acute COPD exacerbation (days) (if completely recovered), COPD medication category (systemic corticosteroids/antibiotics) for treating the acute exacerbation, hospitalisation data, oxygen therapy and ventilation support data, worsening of respiratory symptoms (breathlessness, wheeze, cough, reduction in exercise tolerance, fever, change in sputum production [change in quantity; aspect purulent vs. non purulent], unusual increase of use of “rescue” medication, other worsened symptoms) and COPD exacerbation aetiology (primary and secondary reasons). Likewise, additional investigations performed for acute COPD exacerbation data (microbiology culture, arterial blood gases, chest X-ray, chest CT scan, other) will be summarised by treatment regimen and overall using the ITT and PP populations. For patients who experienced more than one further COPD exacerbation after the initial COPD exacerbation, the most recent COPD exacerbation will be considered for tabulations.

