7.1.3.6 Current COPD exacerbation duration

- Duration of current COPD exacerbation symptoms will be calculated in days as:
(date when symptoms stopped – date when symptoms started + 1)
- Time until complete recovery from the current COPD exacerbation will be calculated in days as:
(date when patient achieved complete recovery from the current exacerbation – date when symptoms started).

Where ‘Date when symptoms started’, ‘Date when symptoms stopped’, and ‘Date when patient achieved complete recovery from the current exacerbation’ are recorded on the ‘Current COPD Exacerbation’ form of the eCRF.

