7.1.4.10 Time to next COPD exacerbation

The time to next COPD exacerbation (in days) is defined as:

(Date when first COPD exacerbation symptoms started – Date when current COPD exacerbation symptoms stopped),

where COPD exacerbations experienced during the study are recorded on the ‘Acute Exacerbation COPD’ form of the eCRF, i.e.:

- Start date of COPD exacerbation is the ‘date when symptoms started’ recorded on the form
- COPD exacerbation has an intensity recorded as ‘Mild’, ‘Moderate’ or ‘Severe’ on the form.

Table 4: Criteria for event/censored for assessment of Time to next COPD exacerbation

Situation	Date of event or Censoring	Time to next COPD exacerbation	Outcome
Subjects who had next COPD exacerbation	Date of next COPD exacerbation after entering in study	Time from when current COPD exacerbation symptoms stopped until Date of next COPD exacerbation after entering in study	Event
Subjects who never had COPD exacerbation in study period	Withdrawal or last contact date	Time from when current COPD exacerbation symptoms stopped until Date of withdrawal or last contact date	Censored
Subjects who died	Death date	Time from when current COPD exacerbation symptoms stopped until Date of death	Censored
Subjects who withdrew or were lost to follow-up during the study	Withdrawal or last contact date	Time from when current COPD exacerbation symptoms stopped until Date of withdrawal or last contact date	Censored

7.1.4.11 Time from hospitalisation admission until subject is medically ready for discharge (current COPD)

This time (in days) will be calculated as:

(Date subject is medically ready for discharge from hospital – Date of hospitalisation admission),

where ‘Date of hospitalisation admission’ and ‘Date subject is medically ready for discharge from hospital’ are recorded on the ‘Current COPD Exacerbation’ form of the eCRF.

Table 5: Criteria for event/censored for assessment of Time from hospitalisation admission until subject is medically ready for discharge (current COPD)

Situation	Date of event or Censoring	Time from hospitalisation admission until subject is medically ready for discharge	Outcome
Subjects who were medically ready for discharge from hospital	Date subject is medically ready for discharge	Time from hospitalisation admission until Time subject is medically ready for discharge	Event

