- Medication started after Study Day 1 (i.e. \geq Randomisation date + 1) and prior to or on completion of the initial treatment (systemic corticosteroids or antibiotics) for the current COPD exacerbation (started no longer than 24 hours before randomisation).

Criterion 3: Worsening of symptoms requiring additional treatment regimen of oral corticosteroids and/or antibiotics after completion of the initial regimen will be derived from the ‘Prior (Last 6 months medication) and Concomitant Medication’ form of the eCRF. The medications recorded on this form to be considered for this criterion will verify:

- Systemic oral corticosteroids (ATC code ‘H02’ and Route ‘PO = oral’) or Antibiotics (ATC code ‘J01’)
- Medication administered for COPD exacerbations only, i.e. with indication = ‘COPD

exacerbation: current/during the study'

- Medication started after completion of the initial treatment (systemic corticosteroids or antibiotics) for the current COPD exacerbation (started no longer than 24 hours before randomisation).

Criterion 4: Re-hospitalisation due to worsening of COPD and requiring additional treatment during the duration of the study due to an exacerbation of respiratory symptoms will be determined based on the COPD exacerbations experienced after the initial study COPD exacerbation and recorded on the 'Acute Exacerbation COPD' form of the eCRF. This criterion will verify:

- "Has the patient experienced any COPD exacerbations after the initial qualifying study exacerbation subsided?" = 'Yes'
- Treatment: Systemic corticosteroids = 'Yes' or Antibiotics = 'Yes'
- Hospitalisation = 'Yes' or (Emergency room = 'Yes' with a admission longer than 24 hours).

Criterion 5: COPD-related death will be determined based on the COPD exacerbations experienced during the study (including the initial study COPD exacerbation) and recorded on the 'Adverse Event' form of the eCRF. This criterion will verify:

- AE Preferred Term 'Chronic obstructive pulmonary disease'
- Serious AE that 'Results in death'.

The cumulative incidence of CTF as well as each of the individual criteria will be evaluated at Day 30, Day 60, Day 90, Day 120, Day 150 and Day 180.

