'A vs B: Visit 4' 0 0 1 0 0 0 0 0 -1 0 0 0 0 0 0 0 0 0,

'A vs B: Visit 5' 0 0 0 1 0 0 0 0 0 -1 0 0 0 0 0 0 0 0,

'A vs B: Visit 6' 0 0 0 0 1 0 0 0 0 0 -1 0 0 0 0 0 0 0,

'A vs B: Visit 7' 0 0 0 0 0 1 0 0 0 0 0 -1 0 0 0 0 0 0,

'A vs C: Visit 2' 1 0 0 0 0 0 0 0 0 0 0 0 -1 0 0 0 0 0,

'A vs C: Visit 3' 0 1 0 0 0 0 0 0 0 0 0 0 0 0 -1 0 0 0 0,

'A vs C: Visit 4' 0 0 1 0 0 0 0 0 0 0 0 0 0 0 0 -1 0 0 0,

'A vs C: Visit 5' 0 0 0 1 0 0 0 0 0 0 0 0 0 0 0 0 -1 0 0,

'A vs C: Visit 6' 0 0 0 0 1 0 0 0 0 0 0 0 0 0 0 0 -1 0,

'A vs C: Visit 7' 0 0 0 0 0 1 0 0 0 0 0 0 0 0 0 0 0 -1,

'B vs C: Visit 2' 0 0 0 0 0 0 1 0 0 0 0 0 0 -1 0 0 0 0 0,

'B vs C: Visit 3' 0 0 0 0 0 0 0 1 0 0 0 0 0 0 -1 0 0 0 0,

'B vs C: Visit 4' 0 0 0 0 0 0 0 0 1 0 0 0 0 0 0 -1 0 0 0,

'B vs C: Visit 5' 0 0 0 0 0 0 0 0 0 1 0 0 0 0 0 0 -1 0 0,

'B vs C: Visit 6' 0 0 0 0 0 0 0 0 0 0 1 0 0 0 0 0 0 -1 0,

'B vs C: Visit 7' 0 0 0 0 0 0 0 0 0 0 0 1 0 0 0 0 0 0 -1 / cl;

LSMESTIMATE trt;

'A vs B: Overall' 1 -1 0,

'A vs C: Overall' 1 0 -1,

'B vs C: Overall' 0 1 -1 / cl;

RUN;

Notes:

- Change represents the change from baseline to each visit of the variable;
- Trt represents the treatment group;
- Visit represents the clinic visit;
- Severity represents the severity of airflow limitation (post-bronchodilator FEV1 at baseline (pre-dose) classified into 2 groups: < 30% or \geq 30% of predicted normal value);
- Eosino represents the blood eosinophils (%) value at baseline (classified into 2 groups: < 2% or \geq 2%);
- Time_symp represents the time from start of current COPD exacerbation symptoms to first IMP dosing (\leq 2 days, 3-4 days or \geq 5 days);
- Cv_comorb represents the cardiovascular comorbidities at screening (presence or absence);
- COPD_trt represents the COPD exacerbation treatment at screening (systemic corticosteroids only, antibiotics only or both systemic corticosteroids and antibiotics);
- Baseline represents the baseline value of the variable;
- ID represents the Patient Number;
- Treatment order: 1 = High dose BCT197, 2 = Low dose BCT197; 3 = Placebo
- the ‘Overall’ least squares means and contrasts will be estimated only for the change from baseline in FEV1.

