8.6.3.12 Number of COPD-related deaths during the study

See section 8.6.3.11 for the derivation of COPD-related deaths.

The proportion of patients with a COPD-related death during the study will be compared between treatment regimens using Fisher’s exact test (two-sided test at 5% alpha level).

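### SAP 8.6.3.12 takes COPD-related deaths from a form and onset-date rule likely to leave out deaths from the index exacerbation, in conflict with the protocol and with treatment-failure Criterion 5

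*SAP*

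**What the plan says.** SAP 8.6.3.12 has no definition of its own: "See section 8.6.3.11 for the derivation of COPD-related deaths". SAP 8.6.3.11 then sets three conditions:

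- The source is the 'Acute Exacerbation COPD' form of the eCRF.
- Only exacerbations with a symptom start date at or after "first study treatment intake on the form will be included in the analysis".
- The death category is "COPD exacerbations resulting in death (i.e. COPD-related deaths; serious criteria" 'Results in death' ticked on that form.

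On the scope of that form, the SAP is not uniform. Criterion 4 in SAP 7.1.4.13 cites the form's question: "Has the patient experienced any COPD exacerbations after the initial qualifying study exacerbation subsided". The closing paragraph of 8.6.3.11 deals with patients who had "more than one further COPD exacerbation after the initial COPD exacerbation". SAP 7.1.3.6 says the dates of the index event "are recorded on the ‘Current COPD Exacerbation’ form of the eCRF", which is a separate form. Against this, SAP 7.1.4.10 says "COPD exacerbations experienced during the study are recorded on the" 'Acute Exacerbation COPD' form. SAP 7.1.4.14 speaks in similarly broad terms and lists, among the data on that form, the date on which an exacerbation assessed as an AE results in death.

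Protocol 11.1 counts COPD-related deaths from first dose to Week 26. Protocol 11.2.4 leaves the attribution to the investigator, with the rationale recorded in the eCRF. Protocol 13.5.3 compares the proportions by Fisher's exact test. None of these excludes the index exacerbation. Criterion 5 in SAP 7.1.4.13 takes COPD-related death from the 'Adverse Event' form and states that the initial exacerbation is included.

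**The concern.** The trial treats a hospitalised exacerbation. A death from that exacerbation is the fatal outcome most directly connected to the treatment under test, yet the rule for the secondary endpoint appears to be written for later exacerbations. If such a death is missed, the reported count and proportion are wrong for the endpoint as the protocol defines it.

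The SAP also tests Criterion 5 on its own in 8.6.4.1. The same report could then show two counts, and two p-values, both labelled as COPD-related death, with no explanation of the difference. SAP Section 9 lists three changes from the protocol (the PP definition, the additional PP analyses, and the steroid-dose window). This is not among them.

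**Working it through.** **Step 1. The definitions side by side.**

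| Place | Source | Onset filter | Who decides that the death is COPD-related | Index exacerbation |
|---|---|---|---|---|
| Protocol 11.1, 11.2.4 | Not tied to a form; rationale in eCRF | None; deaths from first dose to Week 26 | Investigator | Not excluded |
| SAP 8.6.3.11 and 8.6.3.12 | 'Acute Exacerbation COPD' form | Symptom start on or after first dose | 'Results in death' ticked | Not mentioned; depends on form and start date |
| SAP 7.1.4.13, Criterion 5 | 'Adverse Event' form | None stated | COPD preferred term plus 'Results in death' | Expressly included |

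**Step 2. Follow an index death through 8.6.3.11.**

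- *Form condition.* The form's question concerns exacerbations after the initial one subsided. A fatal index exacerbation did not subside. With the reference to further exacerbations in 8.6.3.11 and the separate form in 7.1.3.6, this makes omission likely.
- *Date condition.* An active exacerbation is an entry requirement (Protocol 9.3.1). The notes to the primary model in SAP 8.6.2.1 say "Time_symp represents the time from start of current COPD exacerbation symptoms to first IMP dosing", so index onset comes before dosing or, at the latest, on the same date. If index symptom onset is the recorded start date, the death fails this filter too, unless onset and first dose share a date. If a later deterioration is recorded as a new event, it passes.

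**Step 3. Size.** The plan states no figure for this endpoint and no death rate. The arm size comes from Protocol 13.1: 3 × 85 = 255 evaluable; 255 / 0.95 = 268.4, given as approximately 270 randomised; 270 / 3 = 90 per arm.

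- One omitted death: 1/90 = 1.11%, or 1/85 = 1.18% on the evaluable number.
- If an arm's only COPD-related death came from the index event, it would be reported as 0/90 (Clopper-Pearson 95% CI 0 to 4.0%) instead of 1/90 (1.1%, 95% CI 0.03 to 6.0%).
- Two-sided Fisher's exact test, 90 per arm, for assumed counts against zero: 6 v 0, p = 0.029; 5 v 0, p = 0.059; 4 v 0, p = 0.121; 3 v 0, p = 0.246.
- With a death in the comparator: 8 v 1, p = 0.034; 6 v 1, p = 0.118.

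These counts are assumptions. They show how the test behaves and do not predict how many deaths the trial would see.

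**The case against.** The strongest reply is that a death following the index exacerbation may reach the form after all. Protocol 12.1.1 treats findings before consent as pre-existing and records an AE only when they worsen. Protocol 12.1.2 treats any detrimental change after consent as an AE or SAE and requires a new record when severity changes. A fatal deterioration after dosing could therefore be entered as a new event with onset after first dose, and the date filter would not remove it. SAP 7.1.4.10 and 7.1.4.14 also describe the form as covering exacerbations during the study, and 7.1.4.14 treats it as a source for the date of a fatal outcome. The eCRF that would settle this is not available.

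This stands in part. It weakens the date argument, so the case rests mainly on the form. It does not remove the conflict: Criterion 5 goes to a different form for deaths from the initial exacerbation, and the time-to-next formula in 7.1.4.10 starts when index symptoms stopped, which treats the form's events as later ones.

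Two further replies are correct but limited. Protocol 13.5.1 calls all analyses exploratory, but that does not justify a count that departs from the endpoint's definition. Index deaths also remain visible under Criterion 5 and under AEs leading to death (SAP 8.7.1), but neither feeds the secondary endpoint or its Fisher test.

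**Conclusion.** The point holds as an unreconciled definition with a likely omission. SAP 8.6.3.12 inherits a form and an onset filter that the protocol does not contain, deaths attributed to the index exacerbation are likely to be left out on the form condition, and Section 9 does not disclose the change. Each omitted death costs an arm about 1.1 percentage points at 90 per arm (1.2 at 85).

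A reader might infer more than the documents support:

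- *That index deaths are systematically excluded on both conditions.* The AE recording rules and the broader descriptions of the form leave the extent of omission uncertain.
- *That the test result would change, or that it would not.* With no death rate, neither can be said. If there are few deaths, nothing changes; yet one omission from 6 v 0 moves p from 0.029 to 0.059.
- *That the deaths vanish from the report.* They do not; they are missing from this endpoint.
- *That the protocol's test covers every dosed patient.* Secondary endpoints use the ITT set, which requires a post-baseline FEV1 (Protocol 13.3.1), so a death before that measurement is outside the comparison under any derivation.

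The conclusion assumes that the form question cited under Criterion 4 describes how the form is used in practice.

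**What to change.** In SAP 8.6.3.12, replace the cross-reference with a definition: within the ITT set, every death from first dose to Week 26 that the investigator judged COPD-related under Protocol 11.2.4, index exacerbation included, without the form restriction or symptom-onset filter of 8.6.3.11. Keep Fisher's exact test.

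Criterion 5 already includes the initial exacerbation and need not be redefined. Before unblinding, check that the new count reconciles with Criterion 5 and with the source of the death date in 7.1.4.14, and explain any remaining difference. One is possible because Criterion 5 depends on a preferred term and not on the investigator's attribution.

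If the sponsor wants to keep the narrower count, report it in addition, label it as deaths from new exacerbations, and list it in Section 9.

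The cost is SAP wording and minor programming. The attribution and its rationale are already required in the eCRF. If the attribution is not a coded field, a query to the investigator for each death before unblinding supplies it.
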